## 1.3 Pilot trial of wireless TENS device for CIPN from our group.

We performed a single-site, single-arm pilot study of a wireless TENS device for chronic CIPN.[49] After a baseline screening week to record daily symptoms, the participants were asked either to wear the device for one hour in the morning or one hour in the evening or to wear the device for up to 12 h/day on the continuous setting that alternates between 1h treatment and 1h rest periods. Patient Reported Outcome (PRO) measures were completed at baseline and after 6 weeks, at which time qualitative interviews were performed.

**TENS effects on CIPN:** Our pilot study (n=26 enrolled, 22 completed and included in Table 1 analyses) showed a significant 10% improvement in CIPN (via CIPN20^61, p=0.006). Individual lower limb symptoms (0–10 numeric rating scales (NRSs)) improved considerably (Table 1). Qualitative interviews supported these symptom improvements and the acceptability of the device (Table 2).

Table 2 Qualitative feedback Select quotes

					Table 2. Qualitative Teeuback – Select quotes
	Baseline Mean (SD)	6-week Mean (SD)	P- value	% change	
 
"It helps with pain, swelling everything"
 
"Cured leg cramps"
 

EORTC-CIPN20	40.0 (8.6)	36.0 (10.5)	0.006	-10%	• "You can use it at home, work, or on vacation"
Shooting pain	4.0 (3.3)	2.7 (3.0)	0.015	-33%	"Band is easier to remember than taking pills"     "Can take loss opiates"
Hot-burning pain	3.1 (3.4)	1.5 (2.3)	0.03	-52%	Easier to walk barefoot"
Tingling	5.2 (2.4)	3.9 (2.5)	0.003	-25%	• "Nice to not feel like I am walking on sponges"
Cramping	3.2 (2.9)	1.8 (1.9)	0.002	-44%	"Couldn't feel toes in a pedicure before and     new Lean feel comething in all tops."
Numbness	5.7 (1.6)	4.3 (1.8)	0.0001	-25%	now i can leel something in all toes

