## 10. STATISTICAL CONSIDERATIONS

**10.1 Quality Control.** Established standardized data quality procedures are used for all URCC NCORP Research Base studies. Data will be entered on scannable (Teleforms) or electronic forms in REDCap and electronically transferred to Microsoft Office databases. Data will be inspected visually. Data distributions will be evaluated to identify any outliers that will be inspected for possible mistakes. If no mistake is found for an outlier, it will remain in the data. Statistical analyses will be performed using SAS, JMP, or R as appropriate.

**10.2 Analysis set and Missing Data.** All participants who are randomized will be included in the analyses. All efforts will be made to prevent missing data. We will use multiple imputation methods that assume missing at random for the primary and secondary analyses. A sensitivity analysis using pattern mixture methodology that assumes missing not at random will be used to evaluate the impact of missingness on the results.

**10.3 Sample Size Estimation.** Since this is a phase II preliminary efficacy trial, the primary analysis will be performed at the two-tailed 20% significance level (i.e., alpha=0.2). A sample size of 126 evaluable participants will provide 80% power to detect a 0.4 effect size (standardized mean difference) in the primary analysis. Assuming 15% withdrawal, we will randomize 150 participants.

**10.4 Primary Analysis.** The effects of TENS on CIPN will be estimated using analysis of covariance (ANCOVA). The model will include CIPN20 at Week 6 as the outcome, treatment group as the factor, and study site and the baseline CIPN20 score as covariates. Additionally, to explore potential large impacts of cancer type, chemotherapy class (i.e., platinum, taxane, other), and analgesic consumption ( $\geq$ 30% vs. <30% decrease in number of days acetaminophen and/or NSAIDs were taken), we will add these factors to the above model for sensitivity analyses. We will also perform subgroup analyses separately based on these factors to identify possible differential intervention effects to inform the design of a future study. Distributional assumptions (e.g. normality of residuals) will be evaluated and, if necessary, appropriate transformations or nonparametric methods will be used.

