## 10.6 Exploratory Analyses.

(1) ANCOVA analysis as in the primary will be used to investigate the effects of TENS on exploratory outcomes (i.e., balance (SPPB balance subscale), descending inhibition (CPM test), physical function (PROMIS short form), CIPN-interference in daily life, CIPN measured by TNAS and CIPN symptom inventory composite measure, depression and anxiety (PROMIS short forms)) at baseline and at Week 6 visits.

(2) Analysis of variance (ANOVA) or an appropriate non-parametric method (e.g., Wilcoxon test) if the normality assumption is not satisfied will be used to evaluate the between arm differences in participant-perceived changes in CIPN symptoms and participant-perceived change in ability to be active.

(3) Descriptive statistics will be used to characterize the distribution of descending inhibition as measured by CPM at baseline. Additionally, the correlation of descending inhibition with CIPN severity (via CIPN20, TNAS, and symptom NRS scores) will be evaluated using a Spearman's correlations.

(4) To explore the predictive effects of baseline descending inhibition on response to TENS, ANCOVA analysis will be used to investigate whether baseline descending inhibition predicts the effect of TENS on CIPN. The model will include CIPN20 at Week 6 as the outcome, baseline CPM test result, treatment group, and baseline CPM test result x treatment group interaction as factors, and study site and the baseline CIPN20 score as covariates.

(5) To explore mechanistic associations between changes in descending inhibition and CIPN symptoms, we will use mediation analysis technique (the method initially formalized by Baron and Kenny, extended to clinical trial settings by Kraemer, and methodologically updated by MacKinnon et al.). Specifically, we will use path modeling to estimate indirect (mediation) effects of changes in the CPM test on CIPN symptoms, and bootstrapping to estimate the 95% confidence intervals. The MPlus software will be utilized.

(6) The proportion of participants who decreased "as-needed" usage of acetaminophen and NSAIDs (defined as taking acetaminophen or NSAIDs, on average, at least 30% fewer days per week in the last week of the trial compared to the baseline week) will be compared by groups using a Chi-Square test.

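### Section 10.4 looks for differential effects by cancer type and chemotherapy class through separate subgroup analyses, with no treatment-by-factor interaction, so as written it gives no estimate or CI for the difference between subgroups

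*Combined protocol and SAP*

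**What the plan says.** Section 10.4 specifies an ANCOVA of Week 6 CIPN20 on treatment, with site and baseline CIPN20 as covariates. It then brings in three factors: cancer type (no categories listed), "chemotherapy class (i.e., platinum, taxane, other"), and analgesic consumption, split at a 30% decrease in days of acetaminophen or NSAID use. These are used in two ways. First, "we will add these factors to the above model for sensitivity analyses". Second, "We will also perform subgroup analyses separately based on these factors to identify possible differential intervention effects", with the aim of informing a future study.

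No treatment-by-factor term, between-subgroup contrast or CI for such a contrast is given for these factors in Section 10.4 or in Sections 10.5 to 10.8. Section 10.6(4) does specify an interaction for a different baseline variable: "baseline CPM test result x treatment group interaction as factors". Section 10.6(6) defines a decrease in analgesic use as "at least 30% fewer days per week in the last week of the trial compared to the baseline week", and compares it between arms as an outcome.

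Section 10.3 states that "the primary analysis will be performed at the two-tailed 20% significance level". No level or decision rule is given for subgroups.

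**The concern.** A differential effect is a difference between two treatment effects. Adding a factor as a main effect only adjusts the average treatment effect. Analysing subgroups one by one gives an effect in each, but no stated comparison of them. A reader is then left to compare estimates by eye, or to note that one subgroup reached significance and another did not. Both readings go wrong often when subgroups are small, even if the treatment works equally well in all of them.

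The primary aim of this trial is to inform a phase III design, and these analyses are meant to feed into it. A chance gap between chemotherapy classes could be carried into the next trial, for example as narrower eligibility.

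Analgesic change raises a separate problem. It runs from the baseline week to the last trial week, so treatment can affect it. Participants who cut their analgesic use on active TENS are not comparable with those who cut it on placebo, and the contrast within such a subgroup is no longer a randomised comparison.

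**Working it through.** **Inputs.** From Section 10.3: 126 evaluable, effect 0.4 SD, two-sided alpha 0.20, power 80%. From Section 5.3.4: 1:1 allocation. From Section 1.3 ("n=26 enrolled, 22 completed and included in Table 1 analyses"): CIPN20 went from 40.0 (SD 8.6) to 36.0 (SD 10.5), p = 0.006. Assumed, because the plan gives neither: the subgroup shares and the rule by which subgroups are judged.

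**The plan's own figure.** A two-sample t-test with d = 0.4 and alpha 0.20 needs 57 per arm (114 in total) for 80% power; 126 gives 83%. The stated 126 fits an effect of 0.38 rounded to 0.4. The difference is on the safe side and does not affect this point.

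**Gain from baseline adjustment.** If the pilot p-value is from a paired t-test on 22 people (21 df), t = 3.06. The SD of change is 4.0 × √22 / 3.06, which gives 6.14 from the unrounded t. The correlation is r = (8.6² + 10.5² − 6.14²) / (2 × 8.6 × 10.5) = 0.81, and √(1 − 0.81²) = 0.586. Two cases bracket the answer:

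- Favourable: 0.4 is on the raw SD and r = 0.81, so the effective d is 0.4 / 0.586 = 0.68.
- Unfavourable: 0.4 is unadjusted, or already on the residual scale, so d = 0.4.

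**(a) Comparing estimates by eye.** The true effect is 0.4 SD in every subgroup. For subgroups of n1 and n2, the SE of the difference is √(4/n1 + 4/n2), times 0.586 in the favourable case. Two halves of 63: √(8/63) = 0.356, or 0.209. P(|difference| ≥ 0.4) = 2 × [1 − Φ(0.4/SE)] = 26%, or 6%. For three classes, the chance that the largest and smallest estimates differ by at least 0.4 was simulated.

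**(b) Judging by significance at 20%.** Power p in each subgroup comes from the noncentral t. Halves: p = 0.618 or 0.920, so they disagree in 2p(1 − p) = 47% or 15%. Equal thirds of 42: p = 0.506 or 0.818, so not all agree in 1 − p³ − (1 − p)³ = 75% or 45%.

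| Assumed split | (a) gap ≥ 0.4 SD | (b) significance disagrees |
|---|---|---|
| 50/50 | 6-26% | 15-47% |
| 80/20 | 13-37% | 35-56% |
| three equal | 26-63% | 45-75% |
| 60/25/15 | 36-70% | 60-78% |

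The low end of each range is the favourable case. There is no differential effect in any row.

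**What an interaction would deliver.** Two equal subgroups: 95% half-width 1.96 × 0.356 = 0.70 SD (0.41 favourable). A pair of three equal classes: SE √(8/42) = 0.436, half-width 0.86 SD (0.51 favourable, using a t quantile). Power at the 20% level for a true 0.4 SD difference between two equal subgroups is 44% (74% favourable).

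**The case against.** The strongest reply is that the gap is one of specification. Subgroup estimates with standard errors are independent, so for two subgroups the difference and its SE can be worked out afterwards. That is correct, and the claim is limited to what the plan specifies. But the plan does not say this will be done, and for a three-level factor the choice of contrast matters.

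The plan's word for the subgroup analyses may mean one factor at a time, not one model per stratum. That reading is possible, but it still leaves no between-subgroup contrast.

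The analysis is exploratory and cautiously worded, and the primary estimate is unaffected. This stands and limits the weight of the point. The CPM variable in 10.6(4) is effectively continuous, so an interaction is the natural tool there; its use is a precedent more than an inconsistency.

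The numbers rest on assumed shares and judging rules, and r = 0.81 comes from a reported p-value in 22 completers, with a Fisher 95% interval of about 0.59 to 0.92. This also stands: the percentages are illustrations across a range, and the high ends do not use r at all.

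Finally, an interaction in a trial of this size often cannot separate chance from a real difference. True, but its CI shows that uncertainty, which separate subgroup results leave unstated.

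**Conclusion.** The concern holds. Section 10.4 states an aim, finding differential effects, that its stated method does not deliver, because no between-subgroup contrast is specified. For chemotherapy class, with three levels, a uniform true effect would still produce a gap as large as the whole target effect in roughly a quarter to two thirds of trials. This assumes 126 evaluable, equal or 60/25/15 classes, and a baseline correlation between nil and 0.81. The textual point and the problem with analgesic change need none of these assumptions. The primary analysis is not affected. This is a change that should be made, since it is cheap and serves the plan's own purpose.

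**What to change.** For cancer type and chemotherapy class, which are fixed before randomisation, fit the primary ANCOVA with treatment, factor and treatment × factor, one factor at a time. Base any statement of differential effect on the interaction estimate and its CI. Present subgroup estimates from that same model as descriptive. List the cancer-type categories before unblinding. Include the interaction terms in the multiple imputation model of Section 10.2, so that imputation does not pull the subgroup effects together. Do not interpret subgroups defined by on-trial analgesic change as differential treatment effects; the between-arm comparison in 10.6(6) already covers that variable as an outcome.

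The cost is SAP wording and a small amount of programming, with no change to sample size or data collection. The drawback is the imprecision shown above, which the SAP should state so that a wide interval is not read as evidence of no difference.

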## 10.6 Exploratory Analyses.

(1) ANCOVA analysis as in the primary will be used to investigate the effects of TENS on exploratory outcomes (i.e., balance (SPPB balance subscale), descending inhibition (CPM test), physical function (PROMIS short form), CIPN-interference in daily life, CIPN measured by TNAS and CIPN symptom inventory composite measure, depression and anxiety (PROMIS short forms)) at baseline and at Week 6 visits.

(2) Analysis of variance (ANOVA) or an appropriate non-parametric method (e.g., Wilcoxon test) if the normality assumption is not satisfied will be used to evaluate the between arm differences in participant-perceived changes in CIPN symptoms and participant-perceived change in ability to be active.

(3) Descriptive statistics will be used to characterize the distribution of descending inhibition as measured by CPM at baseline. Additionally, the correlation of descending inhibition with CIPN severity (via CIPN20, TNAS, and symptom NRS scores) will be evaluated using a Spearman's correlations.

(4) To explore the predictive effects of baseline descending inhibition on response to TENS, ANCOVA analysis will be used to investigate whether baseline descending inhibition predicts the effect of TENS on CIPN. The model will include CIPN20 at Week 6 as the outcome, baseline CPM test result, treatment group, and baseline CPM test result x treatment group interaction as factors, and study site and the baseline CIPN20 score as covariates.

(5) To explore mechanistic associations between changes in descending inhibition and CIPN symptoms, we will use mediation analysis technique (the method initially formalized by Baron and Kenny, extended to clinical trial settings by Kraemer, and methodologically updated by MacKinnon et al.). Specifically, we will use path modeling to estimate indirect (mediation) effects of changes in the CPM test on CIPN symptoms, and bootstrapping to estimate the 95% confidence intervals. The MPlus software will be utilized.

(6) The proportion of participants who decreased "as-needed" usage of acetaminophen and NSAIDs (defined as taking acetaminophen or NSAIDs, on average, at least 30% fewer days per week in the last week of the trial compared to the baseline week) will be compared by groups using a Chi-Square test.

(7) The proportion of participants who report, for the impression of change in CIPN symptoms question "very much improved", "much improved", "minimally improved", "no change", "minimally worse", "much worse", and "very much worse") will be compared between treatment groups using a Cochran Armitage Trend Test.

(8) The proportion of participants whose sensation threshold from the monofilament test improved will be reported together with the 95% confidence interval (CI) and tested against the null hypothesis of no improvement.

(9) Descriptive statistics and 95% CIs will be used to assess the percentage of participants and outcome assessors that correctly identify the group to which the participant was assigned as well as the basis for the guesses.

(10)Test, re-test reliability for the CPM test will be evaluated using Intraclass correlation coefficients (ICCs). Test, re-test reliability for the lower limb sensation threshold test will be measured using Kappa statistics.

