# 3. CHARACTERISTICS OF STUDY POPULATION

## 3.1 Inclusion Criteria

Participants must:

- 1. Have completed treatment with a platinum agent, taxane, vinca alkaloid, or bortezomib at least 3 months prior to registration. See Appendix 1 for a list of drugs included in these drug classes.
- 2. Have a clinical diagnosis of CIPN from their physician or physician designee based on the following criteria: bilateral (i.e., present on both sides of the body), abnormal sensory symptoms in their feet or legs (e.g., hot/burning pain, sharp/shooting pain, numbness, tingling, cramping).
- 3. Report at least 1 non-painful symptom associated with CIPN in their lower limbs (e.g., tingling, burning that isn't reported as painful, numbness)
- 4. Report at least 2 of the following symptoms in their lower limbs (at their worst) as at least 4 out of 10 on a 0 10 NRS: hot/burning pain, sharp/shooting pain, numbness, tingling, cramping at Visit 1 (i.e., Week -1). Use the CIPN Symptom Inventory Week Recall form (questions 1-5 ONLY) to assess these symptoms at screening.
- 5. Be willing and able not to start any new analgesic medications or change the dosages of any current analgesic medications (except acetaminophen (Tylenol) or NSAIDs (i.e., ibuprofen (Advil, Motrin), Naproxen (Aleve)) for the duration of the study.
- 6. Be able to read English (i.e., is not illiterate, can speak English, and is not blind).
- 7. Be at least 18 years of age.
- 8. Have access to a smart phone or device with an Apple or Android operating system that can be used to access the TENS device's App and ability to connect to the internet on a daily basis during the trial.

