## 5.3 Schedule of study procedures

# 5.3.1 Screening / Consent Visit (Day -7; -2/+3 days) (approximately 1 hour)

Eligible participants who provide informed consent will be registered and given the daily diary of CIPN symptoms and rescue pain medication consumption, and trained on how to complete it at home during the Baseline Week (i.e., between the Screening and Baseline Visits). They will complete the CPM test and lower limb sensation test. Chemotherapy treatment notes will be collected for all consented participants.

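### The analgesic-reduction comparison in 10.6(6) includes participants with no baseline use, so its proportions and arm difference are diluted by an unreported share of users

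*Combined protocol and SAP*

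**What the plan says.** Section 10.6(6) of the combined protocol and SAP defines a responder on as-needed acetaminophen and NSAID use: "defined as taking acetaminophen or NSAIDs, on average, at least 30% fewer days per week in the last week of the trial" relative to the baseline week. The proportion of such participants "will be compared by groups using a Chi-Square test". The item does not limit the denominator to people who were taking these drugs. Section 10.2 sets the analysis population: "All participants who are randomized will be included in the analyses".

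The entry criteria in 3.1 do not ensure that participants use analgesics:

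- Criterion 3: "Report at least 1 non-painful symptom associated with CIPN in their lower limbs".
- Criterion 4: "Report at least 2 of the following symptoms in their lower limbs (at their worst) as at least 4 out of 10". The list has five symptoms, and numbness and tingling are two of them.
- Criterion 5: "Be willing and able not to start any new analgesic medications or change the dosages of any current analgesic medications". This concerns stability only, and acetaminophen and NSAIDs are exempt from it. No minimum use is set.

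Baseline use will be known. Under 5.3.1, consented participants are "given the daily diary of CIPN symptoms and rescue pain medication consumption" and complete it at home in the week before the Baseline Visit. Randomisation follows once they arrive for that visit (5.3.3).

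The same 30% split appears in 10.4, as a factor added to the primary model in sensitivity analyses and as a subgroup variable. Neither section says how zero baseline days are classified.

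**The concern.** A relative reduction has no meaning when the starting value is zero. A patient with numbness and tingling at 4 out of 10 and no analgesic use is eligible and randomised, yet has no way to become a responder. Staying at zero days is scored the same as going from zero to seven.

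The reported proportions therefore mix two things: how often users cut down, and how many users happened to be enrolled. Only the first bears on whether TENS spares analgesics. The trial exists to give estimates for designing a phase III study (2.1). An absolute difference scaled by an unreported user share is hard to carry forward, and a small one could be read as little sparing effect when it partly reflects few users.

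In 10.4 the lower level of the split has the same problem. It combines people who took nothing at baseline with users who did not cut down.

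**Working it through.** **Inputs.** The documents give no expected rate, power, alpha or user share for this endpoint, so there is no planned figure to reproduce. The following are used:

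- 63 evaluable per arm, from the 126 evaluable in 10.3 divided by 2.
- Assumed: reduction rates among baseline users of p₁ = 45% (active) and p₂ = 25% (placebo), a difference of 20 points.
- Assumed: share of baseline users u = 30%, 50% or 70%, equal in both arms.

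**Formulas.** With non-users as non-responders, the reported rate in an arm is u·p and the reported difference is u·(p₁ − p₂). The unpooled z on n = 63 per arm is

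z = u(p₁ − p₂) / √{[u·p₁(1 − u·p₁) + u·p₂(1 − u·p₂)] / n}.

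In users only, there are n·u per arm and

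z = (p₁ − p₂) / √{[p₁(1 − p₁) + p₂(1 − p₂)] / (n·u)}.

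**Worked case, u = 50%.**

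- As written: 22.5% vs 12.5%. Variance = (0.225×0.775 + 0.125×0.875)/63 = 0.28375/63 = 0.00450; standard error 0.0671; z = 0.10/0.0671 = 1.49.
- Users only: 31.5 per arm. Variance = (0.45×0.55 + 0.25×0.75)/31.5 = 0.435/31.5 = 0.01381; standard error 0.1175; z = 0.20/0.1175 = 1.70.

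**All three cases.**

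| Baseline users | Reported rates | Reported difference | z as written | Difference in users | z in users only |
|---|---|---|---|---|---|
| 30% | 13.5% vs 7.5% | 6 points | 1.10 | 20 points | 1.32 |
| 50% | 22.5% vs 12.5% | 10 points | 1.49 | 20 points | 1.70 |
| 70% | 31.5% vs 17.5% | 14 points | 1.85 | 20 points | 2.01 |

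The planned chi-square uses a pooled variance. At u = 50% the pooled z values are about 1.48 and 1.66, so the comparison does not change materially.

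**What does not change.** The ratio of proportions is the same in both analyses: 22.5/12.5 = 45/25 = 1.8.

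**Power under a second set of assumptions.** Take 75 randomised per arm, users responding 50% vs 30%, and two-sided alpha 0.05 (assumed). With 20%, 40%, 60% and 80% non-users, power is 56%, 40%, 27% and 15% as written, and 61%, 49%, 35% and 20% in users only. The gain is 5 to 9 points.

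**Chance imbalance.** With 40% non-users and 75 per arm, the between-arm difference in non-user share has a standard deviation of √(2×0.4×0.6/75) = 0.08, or 8 points. If 40% of users respond in both arms but the non-user shares are 35% and 45%, the reported rates are 0.40×0.65 = 26% and 0.40×0.55 = 22%. That is a 4-point difference with no difference among users.

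**The case against.** Several points on the other side stand.

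- The proportion of all randomised participants who cut their use is a legitimate quantity and agrees with 10.2. Baseline use is recorded before randomisation, so user shares are equal between arms in expectation. A reader might infer that the comparison is biased or the test invalid. It is not: type I error is preserved, and the noise from chance imbalance is already part of the sampling variance.
- The fall from 20 points to 6, 10 or 14 is mostly a change in what is estimated. The information lost is smaller, as the z values and power figures show.
- A reader might also infer that the rule leaves two codings equally open, because a program testing final days ≤ 0.7 × baseline days would count 0-to-0 as a success. At 50% users that would give 72.5% vs 62.5%. The documents do not support this reading: the definition speaks of a decrease and of fewer days, and 0-to-0 is neither. The alternative is a programming slip to guard against.
- The group at issue is people with no use in one diary week, some of whom may be intermittent users. The documents do not allow them to be described as never having used analgesics.
- Restricting to users does not rescue the test if users are few: power is only 20% with 80% non-users in the second set of assumptions.
- This is one of ten exploratory analyses, named in no aim and with no decision rule.

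These points limit the severity. They do not remove the dilution, and they do not make the reported difference interpretable without the user share.

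**Conclusion.** The concern holds as a minor one. On the plan's own wording, participants with no analgesic days in the baseline week are automatic non-responders, and nothing at entry limits their number. The two proportions and the absolute difference are multiplied by the share of baseline users, some power is lost, and chance imbalance in that share adds noise. The ratio of proportions is unaffected in expectation.

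That the scaling factor equals the user share follows from the definition, given equal shares in the arms. The sizes shown rest on assumed user shares and response rates, none of which is in the documents. The primary and secondary aims do not depend on this endpoint. The only contact with the primary outcome is through the 10.4 sensitivity and subgroup analyses.

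**What to change.** In 10.6(6):

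- Run the chi-square comparison in participants with at least one acetaminophen or NSAID day in the baseline diary week. This selects on a variable fixed before randomisation, so the randomised comparison stays intact.
- State that going from zero to zero days is not a reduction.
- Report by arm the number of baseline non-users and how many of them had started use by Week 6.

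In 10.4, handle zero baseline use the same way, with non-users as a separate category in the factor and in the subgroups.

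The cost is a few sentences in the statistical section, best written before unblinding. The diary data are already collected. The downside is a smaller denominator for this exploratory test.

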### 5.3.4 Randomization/Stratification

A computer-generated randomization schedule will be used to randomize participants 1:1 to the two intervention conditions stratified by study site in random block sizes of 2 and 4. The schedule will be prepared by a URCC NCORP Research Base biostatistician. The coordinator will use the Randomization form in REDCap to obtain the randomization assignment at the Baseline Visit.

The two study arms are as follows:

- a. Active TENS Device
- b. Placebo TENS Device

A total enrollment of 150 participants is planned, with up to 75 participants randomized to each intervention group. Note, that participants who discontinue prior to randomization (i.e., between the screening and baseline visits) will not be replaced. It should take approximately 12 months to accrue all participants.

Week	Screening And Registration	Randomization	Distribution of Study Device	Self- Report Measures	Functional Exam Measures	Coordinator open participant Quell App	Adverse Event Monitoring
Screening (Visit 1)	х						
Baseline (Visit 2)		х	х	Х	Х		
1							Х
2							
3							Х
4							
5							Х
6 (Visit 3)				Х	Х	Х	Х

Table 5. Schedule of Events\*

\*Daily diary completed between screening and baseline visit and during Weeks 4 (i.e., day 21 - 28) and 6 (i.e., day 35 - 42). Participants will be called 4 weeks after the end of the study (i.e., Week 10) and asked if they are using the commercial device).

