# 5.3.6 At home procedures (Days 21-28; 35-42)

Participants will complete a daily diary including the CIPN Symptom Inventory and consumed rescue analgesic medication (i.e., acetaminophen (Tylenol) or NSAIDs). They will be asked to complete it before bedtime when they are not wearing the device during weeks 4 and 6.

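### Section 10.6(6) tests analgesic days only as a yes/no 30% fall with an unadjusted chi-square, which merges increased use with no change and gives no estimate in days

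*Combined protocol and SAP*

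**What the plan says.** Section 5.3.6 has participants record non-prescription analgesic use at home each evening: "Participants will complete a daily diary including the CIPN Symptom Inventory and consumed rescue analgesic medication". The footnote to the Schedule of Events in section 5.3.4 gives the diary weeks: "Daily diary completed between screening and baseline visit and during Weeks 4 (i.e., day 21 - 28) and 6 (i.e., day 35 - 42". A count of days with use is therefore available for the baseline week and for Week 6.

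Section 10.6(6) turns the two counts into one indicator and compares the arms on it: "at least 30% fewer days per week in the last week of the trial compared to the baseline week) will be compared by groups using". The test is chi-square. The section names no covariate, alpha, power or expected rate, and no rule for participants with no use in the baseline week. It is the only between-arm analysis of analgesic use. Section 10.4 uses the same 30% cut, but only as a factor or subgroup in models of CIPN20.

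Other outcomes measured at baseline and Week 6 are treated differently. Section 10.6(1) states: "ANCOVA analysis as in the primary will be used to investigate the effects of TENS on exploratory outcomes". Its list does not include analgesic days. Section 10.5 applies the same ANCOVA to weekly means of the symptom ratings, which come from the same diary.

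**The concern.** A count running from none to all days of a week is cut to yes or no before testing. Three consequences follow from the rule as written, with no outside assumption.

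- **Pooling.** A participant whose use rises is classed with one who does not change and one who falls by less than 30%. The test cannot show that an arm used more.
- **Unevenness.** On small whole numbers, a 30% fall means different things at different baselines.
- **No usable estimate.** The output is a difference in proportions. A phase III design would be better served by a difference in days per week with its CI, and section 2.1 gives informing such a design as the purpose of the efficacy estimates.

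A fourth consequence is likely but needs assumptions to size: a real reduction in use is less likely to be detected.

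**Working it through.** **1. Is there a planned figure to reproduce?** Not for this endpoint. Section 10.3 concerns CIPN20 only: "the primary analysis will be performed at the two-tailed 20% significance level (i.e., alpha=0.2", with a standardized difference of 0.4, 80% power and 126 evaluable. As a check on those inputs, n per arm = 2(z₀.₉₀ + z₀.₈₀)²/0.4² = 2(1.2816 + 0.8416)²/0.16 = 56.3. That rounds up to 57 per arm, or 114 in all. With 63 per arm, power is Φ(0.4 × √31.5 − 1.2816) = Φ(0.963) = 83%. The planned 126 is slightly generous, which has no bearing here. Only the 63 per arm is carried forward.

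**2. The cut on a nominal 7-day week.** The smallest whole-day fall k from baseline b with k/b ≥ 0.30 is:

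| Baseline days | Smallest qualifying fall | Check |
|---|---|---|
| 1, 2, 3 | 1 day | 1/3 = 33.3% |
| 4, 5, 6 | 2 days | 1/4 = 25.0% fails; 2/6 = 33.3% |
| 7 | 3 days | 2/7 = 28.6% fails; 3/7 = 42.9% |

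Going from 1 day to 0 is a response. Going from 7 days to 5 is not.

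**3. Power under assumed scenarios.** None of the following inputs is in the documents. Days with use out of 7 were simulated for 63 per arm from a logit-normal propensity (SD 1.5).

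- Mean logit of use: −1, 0 or 1 (low, middle or high use).
- Never-users: 0% or 30%.
- Correlation of the two weeks' propensities: 0.5 or 0.8.
- Arm effect on the logit scale: 0.6 or 1.0.

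That gives 3 × 2 × 2 × 2 = 24 scenarios, each with 1,200 replicates. The Monte Carlo standard error of a single power is at most √(0.25/1200) = 1.4 points. Participants with zero baseline days were counted as non-responders. The chi-square on the 30% rule was set against ANCOVA of Week 6 days on baseline days. Site effects were not simulated.

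| Scenario | Alpha | Chi-square | ANCOVA | Loss (points) |
|---|---|---|---|---|
| Middle use, 30% never-users, corr. 0.8, effect 0.6 | 0.20 | 52% | 71% | 19 |
| Same | 0.05 | 26% | 45% | 19 |
| Smallest loss at 0.20: high use, no never-users, corr. 0.8, effect 1.0 | 0.20 | 95.6% | 99.5% | 4 |
| Largest loss at 0.20: low use, 30% never-users, corr. 0.5, effect 1.0 | 0.20 | 57.8% | 88.8% | 31 |
| Smallest loss at 0.05: high use, 30% never-users, corr. 0.5, effect 0.6 | 0.05 | 20.9% | 31.1% | 10 |
| Largest loss at 0.05: low use, 30% never-users, corr. 0.5, effect 1.0 | 0.05 | 31.1% | 71.3% | 40 |

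ANCOVA had more power in all 24 scenarios at both levels. The smallest loss at 0.20 arises because both tests are near 100%.

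**4. Where the loss comes from.** In the middle scenario at alpha 0.20, a t-test on the change in days had 67% power. Going from 52% to 67% is the price of the cut. Going from 67% to 71% is the gain from using baseline as a covariate.

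**5. Is it an artefact of non-users?** No. Among baseline users only (two scenarios, correlation 0.7), the loss was 9 to 16 points.

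**6. Validity.** With no arm effect, rejection rates were 21.0% (chi-square) and 20.1% (ANCOVA) at 0.20, and 4.3% and 4.4% at 0.05. Both tests are sound; the difference is efficiency.

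**7. How many are pooled?** In the non-null scenarios, 18% to 35% of participants had more days of use in Week 6 than at baseline, and all were non-responders. This share also depends on the assumptions.

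**The case against.** The strongest reply is that this is item 6 of 10 exploratory analyses, that analgesic use appears in none of the aims in section 2, and that no power is claimed. A responder proportion is easy to read, and the chi-square holds its level. All of that stands and keeps the severity low. It does not supply the missing estimate in days or separate increases from no change.

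A reader might also infer more than the documents support.

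- **That baseline is ignored.** It is not: it is the denominator of every percentage fall. It is only absent as a covariate.
- **That the loss is one known figure, such as 12 to 20 points.** Only 20 of the 48 scenario-by-alpha results fall in that band.
- **That the 0.4 effect size and 20% level in section 10.3 apply here.** They are stated for the primary analysis only.
- **That the 7-day arithmetic is exact.** The screening window of −2/+3 days around Day −7 (section 5.3.1) makes the baseline diary about 4 to 9 days long. Days 35 to 42 are 8 calendar days if counted inclusively. Section 10.6(6) speaks of average days per week, so the rule is a rate. The table of cuts illustrates the unevenness and is not a scoring key.

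Finally, ANCOVA on a bounded proportion with many zeros may fit poorly, and a fallback chosen after seeing residuals is loose. That is fair, and the remedy is to name the alternative and its trigger in advance. A rank-based ANCOVA stayed within about 8 points of the ordinary one and above the chi-square in all 24 scenarios.

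**Conclusion.** The point holds as a minor one. The pooling, the uneven cut and the absence of an estimate in days are properties of the rule and need no assumption beyond a short diary week. The power loss is consistent in direction, but its size rests on assumed usage, correlation and effect: about 4 to 31 points at alpha 0.20 and 10 to 40 at alpha 0.05. It should be quoted only as that range. Nothing here touches the primary or secondary results, and the documents do not support a claim that the planned test is invalid.

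**What to change.** In section 10.6(6), make the between-arm analysis a model of the Week 6 proportion of recorded diary days with acetaminophen or NSAID use, with the baseline-week proportion and study site as covariates, as in 10.6(1). Using recorded days as the denominator also handles diary weeks of unequal length. Name one alternative in advance, either a binomial or quasi-binomial model of days used out of days recorded or a rank-based ANCOVA, and state when it applies. Section 10.4 already allows this kind of fallback. Report the adjusted difference in days per week (7 times the difference in proportions) with its CI.

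Keep the 30% responder proportion by arm as a descriptive line, and state how participants with no baseline use are counted in it. The use of the same cut in section 10.4 is a separate matter that this edit does not change.

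The cost is a sentence or two and no new data. The small downside is that the responder comparison becomes descriptive.
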